8.2. Setting

ARW works with field partners across the US with the same principle of physician-based recruitment for all DSPs. Both physician-level and patient-level data are available for analyses of the migraine DSP (see [Figure 1](#)).

The study population will comprise of consulting patients included in the Migraine VII DSP between May 2022 and November 2022; namely, consulting adult patients diagnosed with migraine and prescribed rimegepant or triptans as an acute treatment for their migraine in the US.

DSP physician participants for the migraine DSP in the US were neurologists and general physicians identified from public lists of healthcare professionals and meeting the following criteria:

- Physicians identified as a PCP or neurologist.
- PCPs must make treatment decisions for at least 10 patients with migraine and neurologists must make treatment decisions for at least 20 patients with migraine.

Candidate respondents were screened online and those who met the predefined eligibility criteria were invited to participate (see [Section 8.2.1](#) and [Section 8.2.2](#)).

[figure not shown]
Each participating physician was asked to provide patient data for up 8 patients with migraine. Patient data for the migraine DSP was based on patients aged 18 years or older with a diagnosis of migraine and not involved in a clinical trial.

As described in Figure 1, during the US survey period (May–November 2022), physicians involved in the management of migraine patients were recruited to complete an online survey (Physician Survey) of their attitudes and behaviors regarding the treatment of migraine. Each physician then completed an electronic Patient Record Forms (PRFs) on 8 consecutive consulting patients with migraine, regardless of the reason for the visit. The consecutive approach to recruitment was stressed to each participating physician to remove the element of selection bias. A generic copy of the data collection forms for Physicians is included in APPENDIX 2. COPIES OF PATIENT RECORD FORM (PRF), PATIENT SELF COMPLETION (PSC) QUESTIONNAIRES and PHYSICIAN SURVEY QUESTIONNAIRES: ENGLISH LANGUAGE VERSION.

The patients were then asked if they would be willing to complete a pen-and-paper Patient Self-Completion (PSC) questionnaire about their experiences of having migraine. This allows a unique view of the disease from both the patient and physician perspective. Completion of the PSC by the patient was voluntary.

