8.5. Study Size

Given the primary research objective is purely descriptive in nature (i.e., no *a priori* hypotheses specified), the available sample size is fixed by the DSP data collection methodology and simply impacts the precision of any estimates. Therefore, formal sample size calculations are not applicable and have not been performed. All patients who meet the eligibility criteria will be included in the study. For this study, the sample size is 528 (91 Rimegepant, 437 Triptans) for the physician-reported outcomes, and 143 (29 Rimegepant, 113 Triptans) for the patient-reported outcomes. Data Management

Pseudoanonymised data are taken from the Migraine VII DSP, which is owned and managed by ARW.

All data analysis will be conducted using Stata 17 software, version 17.0 (StataCorp, College Station, Texas) / IBM® SPSS® Data Collection Survey Reporter v7.5 or the latest available version at time of analysis. All programming code/ syntax written to conduct the required analysis will be logged for transparency and replicability.

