8.6. Data Analysis

Analyses will be based on patients receiving rimegepant or triptans only as an acute treatment currently for their migraine.

Data will be stratified by time spent on rimegepant or triptans and number of migraine related headache days.

Analysis will be descriptive. The mean, standard deviation (SD), median, 25th and 75th percentiles and minimum and maximum values will be reported for numeric variables, whilst relative frequencies and percentages will be reported for categorical variables.

The real-world nature of the DSP means many variables will contain missing data. We would expect the base of patients to vary from variable to variable due to imperfect physician knowledge, physicians not wishing to answer the question, etc. The base relevant to each analysis will be reported in any data tables provided. There will be no imputation of missing data. Where missing values are found in a particular variable, any patients with missing values will be removed from all pieces of analysis where that variable is used. However, patients removed from one piece of analysis are still eligible for inclusion in other analyses. In the derivation of PRO variables, the handling of missing data will follow the official instructions as provided by the author/owner of the PRO questionnaire.

Detailed methodology for summary and statistical analyses of data collected in this study is documented in a statistical analysis plan (SAP) below:

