Satisfaction with current acute treatment (patient perspective)	PSC HQ18a	
Proportion of responses to: Extremely satisfied / Satisfied / Slightly Satisfied / Neither satisfied nor dissatisfied / Slightly dissatisfied / Dissatisfied / Extremely dissatisfied
 
Satisfaction will be defined as responses to: 'Extremely satisfied' or 'Satisfied' or 'Slightly Satisfied' combined
 
Dissatisfaction will be defined as responses to: 'Neither satisfied nor dissatisfied' or 'Slightly dissatisfied' or 'Dissatisfied' or 'Extremely dissatisfied' combined
 
Data to be matched to PRF equivalent data (PRF IQ1a)

Drivers for lack of satisfaction with current acute treatment (patient perspective)	PSC HQ18b	
Proportion of responses to: It only reduces my migraine pain by half / It reduces my migraine pain by less than half / It does not work quickly enough / It does not work as well as it used to / The number of side effects I experience / The severity of the side effects I experience / I am not happy with the way I have to take it / I find it difficult to know when to take it / I have too many different acute treatments to take / I worry about becoming dependent on it / It costs me too much money / Other

8.6.4. Analysis for Objective 3

Objective 3 focuses on willingness of patients to continue taking rimegepant or triptans to treat their migraine attacks. This will be addressed by describing the following:

Variable	Data Source(s)	Analysis Plan
Patient willingness to continue use of acute treatment (patient perspective)	PSC HQ18c	
Proportion of responses to: Definitely yes / Probably yes / Do not know / Probably not / Definitely not
 
Responses of "Don't know" will be omitted from analysis.
 
Willingness to continue will be defined as responses to: 'Definitely yes' or 'Probably yes' combined
 
Unwillingness to continue will be defined as responses to 'Probably not' and 'Definitely not' combined

8.6.5. Analysis for Objective 4

Objective 4 focuses on the proportion of those treating acutely with rimegepant or triptans that are optimised on their treatment. This will be addressed by describing the following:

Variable	Data Source(s)	Analysis Plan
Migraine Treatment Optimization Questionnaire (m-TOQ6)	PSC Section I- m-TOQ6	Reported by proportion of responses per time item and total score. The official m-TOQ6 scoring algorithm will be used to calculate total score.

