8.8. Limitations of the Research Methods

- Physicians are asked to provide data on consecutively consulting patients who meet the eligibility criteria, thus reducing the chance of any selection bias on the consulting population by physicians. However, generalisability of the study results to the wider patient population will be impacted as follows:
 - Participants from the Migraine VII DSP (from which the study population is drawn) do not constitute a true random sample, more a pragmatic (physicians) and pseudo-random (patients) sample, and although minimal selection criteria were imposed to identify physicians for inclusion, participation is influenced by the willingness to complete the record forms.
 - The patient sample may be more severely affected by their disease and/or treatment due to their consulting nature (ie, a requirement for inclusion in the Migraine VII DSP). Furthermore, patients who consult more frequently are more likely to be included in the patient sample. However, physicians were asked to provide data for a number of consecutively consulting patients meeting the Migraine VII DSP inclusion criteria to reduce selection bias.

- No patient selection verification procedures were applied to the Migraine VII DSP, and identification of the participants included was based on physician judgement/ perception rather than formal medical coding (eg, diagnostic codes). Nevertheless, this process is representative of physicians' real-world classification of their patients.
- The cross-sectional design of the DSP does not allow for causal relationships; however, identification of associations is possible.
- Physicians and patients were requested to capture patient information retrospectively within the PRF and PSC respectively, which may introduce recall bias – a common limitation of survey data. However, physicians did have the ability to refer to the patients' medical records while completing the PRF, thus minimising the possibility of recall bias. Moreover, most questions within the PSC have a limited recall period to further minimise the risk of recall bias.

Study data are self-reported by participants (eg, physicians and patients) as no independent verification was possible due to the nature of the ARW DSP methodology.

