8.9. Other Aspects

Strengths of this research methods are:

- Dataset provides the physicians' actual treatment and prescribing decisions.
- The DSP is a pseudo-random sample. The methodology used (collecting next n consulting patients) aims to reduce the likelihood of selection bias, and the sample should be representative of the consulting population.
- The dataset is an independent data source providing impartiality of data reporting with no set hypotheses at design stage.
- The DSP includes all consulting patients, covering both insured and non-insured patients. Each patient is unique and there is no double-representation.
- Amongst the variables collected, importantly, the DSP specifically includes, via the physician-completed record form, clinical characteristics, the patient's complete treatment history from diagnosis to current day and reasons for prescribing / stopping treatment.

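### All patient-reported outcomes come from a voluntary questionnaire available for about 27% of patients; the plan never compares completers with the rest, and Section 8.9 does not exempt them from its representativeness statement

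*Combined protocol and SAP*

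**What the plan says.** Under Section 8.2, each physician filled in a Patient Record Form (PRF) for a run of consecutive patients, who were then invited to complete the PSC on paper. The section adds: "Completion of the PSC by the patient was voluntary".

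Table 1 and Sections 8.6.2 to 8.6.5 take these outcomes from the PSC alone:

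- HQ6, the number of attacks in five with pain freedom at two hours
- HQ18a to HQ18c, on satisfaction, reasons for dissatisfaction and willingness to continue
- m-TOQ6
- HQ3 and HQ4a, on when and how often the drug is taken

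Section 8.5 gives 528 patients (91 rimegepant, 437 triptans) for physician-reported outcomes and "143 (29 Rimegepant, 113 Triptans) for the patient-reported outcomes".

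Section 8.6 uses available cases without imputation: "any patients with missing values will be removed from all pieces of analysis where that variable is used". It reports the base for each table and says bases will vary "due to imperfect physician knowledge, physicians not wishing to answer the question, etc". It stratifies by time on drug and headache days, not by PSC status.

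Section 8.8 says that consecutive recruitment works by "thus reducing the chance of any selection bias on the consulting population by physicians", and concedes that "participation is influenced by the willingness to complete the record forms". Section 8.9 lists as a strength that "the sample should be representative of the consulting population".

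**The concern.** A reader can work out from Sections 8.2 and 8.5 and the table bases that the patient-reported results describe completers. What the reader cannot learn is who the completers are. A base shows how many answered, not how they differ from those who did not.

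The consecutive-patient argument protects against physicians choosing patients. It has no bearing on which patients then return a voluntary questionnaire. Section 8.5 treats the fixed sample size as a matter of precision only, but non-response bias does not shrink as the sample grows.

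The patient view for Objectives 1 and 2, all of Objectives 3 and 4, and research question 5 rest on this subset. The research questions are worded for patients on these drugs in general. HQ6 is also the only listed outcome that counts attacks, so the patient-level evidence on reliability across attacks depends on it. The amendment log says the triptan analysis was added to support a reimbursement submission in China, so readers outside the study team may rely on these figures.

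**Working it through.** **Stated counts (Section 8.5).** Physician-reported: 91 + 437 = 528, as stated. Patient-reported: 29 + 113 = 142, against 143 stated.

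**Share with patient-reported data.**

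| Group | With PSC | Without PSC | Share with PSC (Wilson 95% CI) |
|---|---|---|---|
| Rimegepant | 29 | 91 − 29 = 62 | 29/91 = 31.9% (23.2% to 42.0%) |
| Triptans | 113 | 437 − 113 = 324 | 113/437 = 25.9% (22.0% to 30.2%) |
| Both | 142 | 528 − 142 = 386 | 142/528 = 26.9% |

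With the stated total, the overall share is 143/528 = 27.1%. If the missing patient belongs to one group, its share becomes 30/91 = 33.0% or 114/437 = 26.1%. The argument does not depend on which is right.

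The shares do not differ clearly between groups (Fisher p = 0.24). That says nothing about whether completers resemble non-completers.

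**Bias from self-selection.** In a group, bias = (1 − share with data) × (completer rate − non-completer rate). The documents give no value for the difference, so 10 and 20 points are assumed.

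- Rimegepant: 0.6813 × 0.10 = 6.8 points; 0.6813 × 0.20 = 13.6 points.
- Triptans: 0.7414 × 0.10 = 7.4 points; 0.7414 × 0.20 = 14.8 points.

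For scale, the 95% sampling half-width at a proportion of 50% is:

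- Rimegepant: 1.96 × √(0.25/29) = 18.2 points.
- Triptans: 1.96 × √(0.25/113) = 9.2 points.

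**Effect on the contrast (rimegepant minus triptans).**

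- Equal differences in both groups: the biases nearly cancel, and the contrast moves by only 0.6 to 1.2 points.
- 20 points for rimegepant and 10 for triptans: 13.63 − 7.41 = +6.2 points.
- 10 points for rimegepant and 20 for triptans: 6.81 − 14.83 = −8.0 points.

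**Bounds with nothing assumed about non-completers.** If 70% of completers succeeded (assumed), the rate among all eligible patients lies between 0.70 × share and 0.70 × share + (1 − share). That is 22% to 90% for rimegepant and 18% to 92% for triptans.

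**Precision of a completer v non-completer table, at 50%.**

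- Rimegepant: 1.96 × √(0.25 × (1/29 + 1/62)) = 22.0 points.
- Triptans: 1.96 × √(0.25 × (1/113 + 1/324)) = 10.7 points.
- Clustering by physician: design effect = 1 + (m − 1) × ICC. Assuming m from 2 to 8 (8 is the maximum per physician in Section 8.2) and ICC from 0.05 to 0.10, it runs from 1.05 to 1.70. The half-widths become 22.6 to 28.7 points (rimegepant) and 11.0 to 14.0 points (triptans). The inflation is smaller if completion varies within physicians.

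**Chance findings.** Nine variables in two groups give 18 comparisons. At the 5% level, 18 × 0.05 = 0.9 intervals would exclude zero by chance. If the comparisons were independent, the probability of at least one is 1 − 0.95^18 = 60%.

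**The case against.** The strongest reply is that the representativeness sentence in Section 8.9 is tied to consecutive sampling, says only that the sample should be representative, and is never applied to PSC results. Much is also disclosed: the voluntary form, separate sample sizes, table bases, and a limitation on willingness to complete the record forms. The bias figures are assumed, and for rimegepant they are smaller than the sampling half-width. The proposed table is imprecise and would not change any planned analysis. The documents also do not say how much of the shortfall is patient refusal.

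Part of this stands. Section 8.9 makes no explicit false claim about completers. The magnitudes are illustrations, the cause of the shortfall is not established, and the upper design effect needs all eight of a physician's patients to fall in one treatment group. Clustered intervals go beyond what a purely descriptive plan strictly needs.

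It does not answer the main point. The limitation in Section 8.8 most naturally refers to the physician-completed record form; even read broadly, it does not describe completers. Nothing in the plan addresses self-selection into the PSC subset, and Section 8.9 leaves the reader free to carry the representativeness statement over to it.

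**Conclusion.** The concern holds. Patient-reported results rest on a self-selected subset of about 27%, with no planned description of how it differs from the rest and no exception in the representativeness statement. This should be changed.

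The counts are firm, apart from the one-patient discrepancy in the patient-reported total. The direction and size of any bias are unknown. Under assumed differences of 10 to 20 points, the bias is below the sampling half-width for rimegepant and close to or above it for triptans. The between-drug contrast is largely protected if selection works alike in both groups, and not otherwise.

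The 143 against 142 mismatch is a separate correction and adds no weight to the bias argument.

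**What to change.** 1. Add to Section 8.6 a descriptive table, within each treatment group, of patients with and without a PSC: age, sex, attack severity, headache days, chronic status, time on drug, preventive use, DQ18 (physician-reported failure of pain freedom) and IQ1a (physician-rated satisfaction). Show bases and Unknown counts. Preferably add 95% confidence intervals for the differences that allow for clustering by physician; a plain table is the minimum. Label it as added after the Version 1.0 tables. Use it to describe completers, not as a test that triggers or waives anything.
2. Name PSC non-completion in Section 8.8, limit the representativeness sentence in Section 8.9 to the PRF sample, and word every patient-reported conclusion as applying to PSC completers, whatever the table shows.
3. Reconcile 143 with 29 + 113 = 142 in Section 8.5.

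The cost is one table and three or four sentences. No new data are needed: the PRF variables are already planned, and Section 8.6.3 already matches IQ1a to HQ18a, so for that variable only the non-completer column is missing. The drawback is imprecision, chiefly for rimegepant, and more so where DQ18 is Unknown. Similarity on PRF variables would not prove similarity on HQ6 or m-TOQ6, which is why the wording changes should not depend on the table.

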8.2.1. Inclusion Criteria

Patients must meet all of the following inclusion criteria to be eligible for inclusion in the final study population for analysis:

1. Patients who have episodic and/or chronic migraine
2. Patients age >18
3. Currently prescribed rimegepant OR triptans for the acute treatment of migraine

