8.2.2. Exclusion Criteria

Patients meeting any of the following exclusion criteria will not be included in the study population for analysis:

1. Currently prescribed rimegepant for prevention of migraine or for both the acute treatment & prevention of migraine
2. Rimegepant group: currently prescribed an acute treatment for migraine other than rimegepant
3. Triptan Group: currently prescribed an acute treatment for migraine other than triptans

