Current comorbidities			Myocardial infarction / Ischaemic stroke / Haemorrhagic stroke / TIA / Cerebrovascular disease / Hypertension / Hypotension / Ischaemic heart disease / Congestive heart failure / Atrial fibrillation / Arrhythmia / Angina / Deep vein thrombosis / Cardiomyopathy / Coronary artery disease / Peripheral vascular disease / Mitral valve disease / Reynaud's disease / Type 1 diabetes (with and without complications) / Type 2 diabetes (with and without complications) / Obesity / Thyroid disease / Hyperlipidaemia / Dyslipidaemia / Mild/Moderate/Severe renal disease / Mild/Moderate/Severe liver disease / NASH / Depression / Anxiety / Stress / Vascular dementia / Alzheimer's disease / Other dementia / Epilepsy / Parkinson's disease / Obsessive compulsive disorder / Panic disorder / Sleeping disorders / Seizures / Vertigo / Chronic pulmonary disease / Asthma / Chronic sinusitis / Connective tissue disease / Hemiplegia/Paraplegia / Rheumatologic disease / Arthritis / Neuropathic pain / Osteoporosis / Neck pain / Back

Table 1. Variables

Variable	Purpose	Data Source(s)	Operational Definition
			pain / Fibromyalgia / Trigeminal neuralgia / Muscle weakness / Any malignancy / Metastatic solid tumour / Tumour without metastases / Gastrointestinal problems / Peptic ulcer disease / Lupus / Anorexia / Alcoholism / Menstrual disorders / IBS / Glaucoma / AIDS/HIV / Erectile dysfunction / Long term effects of COVID-19 / Other / None
Patient received prior acute treatment(s)	Patient current & prior acute treatments	PRF DQ10	Triptan(s) including combinations / NSAID(s) including combinations / Anti-CGRP gepants / Opioid analgesics including combinations / Non-opioid analgesics including combinations / Ergotamines and Derivatives / Serotonin 5-HT1F agonist (ditan) / Other / No drug treatment
Time spent on Rimegepant or triptans (currently receiving)		PRF DQ2a	Days / Don't know
Patient current preventive treatment(s)	Patient current & prior preventive treatment (s)	PRF EQ1 PRF EQ3 PRF EQ10	Yes / No but previously / Never
Patient prior prevention treatment(s)			
Failure to achieve pain freedom within 2 hours post dose (physician perspective)	Outcome-Objective 1	PRF DQ18	Yes / No / Unknown

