Drivers for lack of satisfaction with current acute treatment (patient perspective)	Outcome-Objective 2	PSC HQ18b	It only reduces my migraine pain by half / IT reduces my migraine pain by less than half / It does not work quickly enough / It does not work as well as it used to / The number of side effects I experience / The severity of the side effects I experience / I am not happy with the way I have to take it / I find it difficult to know when to take it / I have too many different acute treatments to take / I worry about becoming dependent on it / It costs me too much money / Other
Patient willingness to continue use of acute treatment (patient perspective)	Outcome-Objective 3	PSC HQ18c	Definitely yes / Probably yes / Do not know / Probably not / Definitely not

Table 1. Variables

Variable	Purpose	Data Source(s)	Operational Definition
Migraine Treatment Optimization Questionnaire (m-TOQ6)	Outcome-Objective 4	PSC Section I- m-TOQ6	Reported by item and total score.
When patient takes acute Rx treatment	Outcome – Objective 5	PSC HQ3	Before any sign of a migraine attack, but in anticipation of one starting / At the first sign of a migraine attack (before the pain starts) / When the pain starts / After the pain has started and I have an idea of how severe it is
How many days per month patient takes acute Rx treatment	Outcome – Objective 5	PSC HQ4a	

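### Eligibility asks only for a current prescription, so a patient started or switched at the survey visit may be counted under a drug not yet used

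*Combined protocol and SAP*

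**What the plan says.** Inclusion criterion 3 in Section 8.2.1 is "Currently prescribed rimegepant OR triptans for the acute treatment of migraine". Neither Section 8.2.1 nor Section 8.2.2 sets a minimum time on the drug or a minimum number of treated attacks. The group-specific exclusions concern only other current acute prescriptions, for example "Triptan Group: currently prescribed an acute treatment for migraine other than triptans".

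Section 8.2 has each physician complete record forms (PRFs) on "8 consecutive consulting patients with migraine, regardless of the reason for the visit". It continues: "The patients were then asked if they would be willing to complete a pen-and-paper Patient Self-Completion (PSC) questionnaire".

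Section 8.6 words the base differently: "Analyses will be based on patients receiving rimegepant or triptans only as an acute treatment currently for their migraine". It adds: "Data will be stratified by time spent on rimegepant or triptans and number of migraine related headache days". No cut-points are given for either factor.

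Table 1 (Section 8.3) lists PRF item DQ2a, "Time spent on Rimegepant or triptans (currently receiving"), recorded in days or Don't know. Section 8.6.1 omits the Don't know responses when that variable is analysed.

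**The concern.** Being prescribed a drug and having used it are different things for one kind of patient: the one whose acute drug is first prescribed, or changed, at the visit where the survey forms are completed. Recruitment does not screen such visits out.

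Most outcomes presuppose use. They cover pain freedom per five attacks, satisfaction, willingness to continue, treatment optimisation, timing of intake and days of use per month. As labelled in Table 1, none of the patient items names a drug; HQ4a, for instance, is "How many days per month patient takes acute Rx treatment". A patient moved from a triptan to rimegepant that day has no experience of rimegepant to report.

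Amendment 1 adds triptans so that the two drugs can be described against each other for a reimbursement submission. If some answers about one drug appear under the other, that display is affected, and a patient switched because the old drug failed would carry that failure into the new drug's column. The limitations in Section 8.8 do not mention this.

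**Working it through.** **1. Can a patient who starts or switches at the visit pass the written rules?** Take a patient changed at the visit from a triptan to rimegepant alone.
- Criterion 3 is met for rimegepant once the prescription is written.
- The rimegepant-group exclusion is not triggered, because no other acute drug is now prescribed.
- The triptan-group exclusion is likewise not triggered by a change in the other direction.

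So the rules do not exclude such a patient. Whether the patient is recorded under the new drug depends on whether current status is fixed before or after that visit's prescribing decision. The documents do not say.

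**2. What could happen to the answers?**
- Status recorded as on arrival: the patient stays under the old drug and nothing is misassigned.
- Recorded under the new drug, answers about the old one: misassigned.
- Recorded under the new drug, answers without experience: uninformative. HQ6, HQ18a and IQ1a list no Don't know option, and Sections 8.6.2 and 8.6.3 count 0 of 5 attacks as not a success and a neutral satisfaction answer as dissatisfaction.
- Items left blank, or Unknown/Do not know chosen on DQ18 or HQ18c: dropped from that table, giving a smaller base.

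**3. Does the stratification resolve it?** Without cut-points, the shortest stratum may mix same-day starters with genuine early users. Patients with DQ2a recorded as Don't know leave the stratified tables but stay in the overall ones. The overall estimates include everyone.

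**4. Size.** Section 8.5 gives 528 physician-reported records (91 + 437 = 528, reproduced) and 143 patient-reported records (29 + 113 = 142, one short of the stated total). I use the group counts as denominators.

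One patient's weight in a proportion:
- Patient-reported: 1/29 = 3.4 points for rimegepant; 1/113 = 0.9 points for triptans.
- Physician-reported: 1/91 = 1.1 points; 1/437 = 0.2 points.

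For a share f of misassigned patients, observed proportion = (1 − f) × p_new + f × p_old, so bias = −f × (p_new − p_old). The documents give neither f nor the success rates. The values below are assumptions.

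| f | of 29 | of 113 | bias, 60% vs 30% | bias, 60% vs 50% |
|---|---|---|---|---|
| 5% | 1.5 | 5.7 | −1.5 points | −0.5 points |
| 10% | 2.9 | 11.3 | −3.0 points | −1.0 points |
| 20% | 5.8 | 22.6 | −6.0 points | −2.0 points |

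As a count: 3 of 29 with 20% success against 60% gives (3/29) × 40 = 4.1 points. The sign reverses if the earlier drug did better than the new one.

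For scale, the 95% Wilson half-width at 50% is about 17 points for n = 29 and 9 points for n = 113.

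**The case against.** A reader might infer that patients switched at the visit are in fact credited to the new drug, and that answers are misassigned across every objective. The documents do not support that, for these reasons.
- The moment at which current status is fixed is not stated, and the questionnaire wording is in an appendix that is not part of the text available here.
- HQ18a, HQ18b and IQ1a are labelled as referring to the current acute treatment, which ties them to the classifying drug.
- DQ18 and HQ18c offer an Unknown or Do not know response, which the analysis omits; blank items are also dropped.
- FQ1a, an Objective 1 outcome, can be answered for a drug prescribed that day.
- Section 8.6 speaks of patients receiving the drug and can be read as narrowing the base to users.
- The size is wholly assumed, and the illustrated shifts are small against the sampling uncertainty at n = 29 in a purely descriptive study.

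All of this stands against the stronger reading, and the opportunity remains. No written rule requires prior use. The word receiving in Section 8.6 is not turned into a filter, and several outcomes have no Don't know option. The wide interval at n = 29 is no full answer, because a sampling interval does not cover bias.

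**Conclusion.** The point holds as a gap in the definition of the exposed population. The plan allows a patient who had not used the drug before the survey visit to contribute experience-based answers under it, and the overall tables would not show this. It does not establish that misassignment occurred, nor how often.

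The size is known only per patient: up to 3.4 points in the rimegepant patient-reported tables and 0.9 points in the triptan ones. Under assumed shares of 5% to 20% and the two assumed contrasts tabulated above, the shift is 0.5 to 6 points. The affected items are DQ18, IQ1a, HQ3, HQ4a, HQ6, HQ18a-c and m-TOQ6; FQ1a is outside the point. The case for acting rests on the low cost of the remedy, since the variable that would reveal these patients is already collected.

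**What to change.** - In Sections 8.2.1 and 8.6, use one definition: for this analysis, currently prescribed means in use before the survey visit.
- Limit the experience-based outcome tables (the items listed in the verdict) to patients whose DQ2a shows use before that visit. First check how same-day starts are coded; the documents do not show that they are coded as 0 days. Apply the filter to DQ2a in days, since Section 8.6.1 allows conversion to weeks or months, which could hide them.
- Report the number removed per drug, and show patients with DQ2a recorded as Don't know on a separate line.
- Pre-specify the DQ2a strata so that short-exposure patients are visible.
- Patient-characteristic tables and FQ1a can keep everyone.
- Optional: a sensitivity table in longer-exposed patients, for example at least 90 days, with its base reported. That cut-off is a choice; the documents state no 3-month look-back for HQ6, HQ18a or m-TOQ6.

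The cost is one filter on an existing variable and a slightly smaller base in the outcome tables. If nobody started at the survey visit, the count removed will show that. DQ2a cannot prove that an attack was treated, so the filter removes only the clearest cases.
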